### 10.1.4 Data Protection

All personal data collected related to participants, Investigators, or any person involved in the study, which may be included in the Sponsor's databases, shall be treated in compliance with all applicable laws and regulations including the GDPR (Global Data Protection Regulation).

Data collected must be adequate, relevant and not excessive, in relation to the purposes for which they are collected. Each category of data must be properly justified and in line with the study objective.

Subject race and ethnicity will be collected in this study as part of the data comprising the baseline characteristics of the population.

- Participants will be assigned a unique identifier by the Sponsor. Any participant records or datasets that are transferred to the Sponsor will contain the identifier only; participant names or any information which would make the participant identifiable will not be transferred.
- The participant must be informed that his/her personal study-related data will be used by the Sponsor in accordance with local data protection law. The level of disclosure must also be explained to the participant.
- The participant must be informed that his/her medical records may be examined by Clinical Quality Assurance auditors or other authorized personnel appointed by the Sponsor, by appropriate IRB/IEC members, and by inspectors from regulatory authorities.
- When archiving or processing personal data pertaining to the Investigator and/or to the participants, the Sponsor shall take all appropriate measures to safeguard and prevent access to this data by any unauthorized third party.

### 10.1.5 Committees Structure

An ARAC, a committee of experts in the field of allergology and diabetes mellitus independent from the Sponsor and the Investigators, blinded for the treatment groups, will adjudicate hypersensitivity reactions, hypersensitivity-like reactions, and events of potential loss of efficacy, according to criteria as defined in the ARAC charter. The ARAC members may recommend additional follow-up (ie, AIA titers measurement) after the end of study per SoA ([Section 1.3](#)) in specific participants with treatment-emergent AIAs at the end of study with potential impact on glycemic control or safety. Details of these activities and assessments are being outlined in the ARAC charter.

### 10.1.6 Dissemination of Clinical Study Data

Sanofi shares information about clinical trials and results on publically accessible websites, based on company commitments, international and local legal and regulatory requirements, and other clinical trial disclosure commitments established by pharmaceutical industry associations. These websites include [clinicaltrials.gov](http://clinicaltrials.gov), EU clinical trial register ([eu.ctr](http://eu.ctr)), and [sanofi.com](http://sanofi.com), as well as some national registries.

In addition, results from clinical trials in patients are required to be submitted to peer-reviewed journals following internal company review for accuracy, fair balance and intellectual property. For those journals that request sharing of the analyzable data sets that are reported in the publication, interested researchers are directed to submit their request to [clinicalstudydatarequest.com](http://clinicalstudydatarequest.com).

Individual participant data and supporting clinical documents are available for request at [clinicalstudydatarequest.com](http://clinicalstudydatarequest.com). While making information available we continue to protect the privacy of participants in our clinical trials. Details on data sharing criteria and process for requesting access can be found at this web address: [clinicalstudydatarequest.com](http://clinicalstudydatarequest.com).

### 10.1.7 Data Quality Assurance

- All participant data relating to the study will be recorded on printed or electronic CRF unless transmitted to the Sponsor or designee electronically (eg, laboratory data). The Investigator is responsible for verifying that data entries are accurate and correct by physically or electronically signing the CRF.
- The Investigator must maintain accurate documentation (source data) that supports the information entered in the CRF.
- The Investigator must permit study-related monitoring, audits, IRB/IEC review, and regulatory agency inspections and provide direct access to source data documents.
- The Sponsor or designee is responsible for the data management of this study including quality checking of the data.
- Study monitors will perform ongoing source data verification to confirm that data entered into the eCRF by authorized site personnel are accurate, complete, and verifiable from source documents; that the safety and rights of participants are being protected; and that the study is being conducted in accordance with the currently approved protocol and any other study agreements, ICH GCP, and all applicable regulatory requirements.

- Records and documents, including signed ICFs, pertaining to the conduct of this study must be retained by the Investigator for at least 15 years after the end of the clinical study unless local regulations or institutional policies require a longer retention period. No records may be destroyed during the retention period without the written approval of the Sponsor. No records may be transferred to another location or party without written notification to the Sponsor.

#### **10.1.8 Source documents**

- Source documents provide evidence for the existence of the participant and substantiate the integrity of the data collected. Source documents are filed at the Investigator's site.
- Data reported on the CRF or entered in the eCRF that are transcribed from source documents must be consistent with the source documents or the discrepancies must be explained. The Investigator may need to request previous medical records or transfer records, depending on the study. Also, current medical records must be available.

#### **10.1.9 Study and site closure**

The Sponsor or designee reserves the right to close the study site or terminate the study at any time for any reason at the sole discretion of the Sponsor. Study sites will be closed upon study completion. A study site is considered closed when all required documents and study supplies have been collected and a study-site closure visit has been performed.

The Investigator may initiate study-site closure at any time, provided there is reasonable cause and sufficient notice is given in advance of the intended termination.

Reasons for the early closure of a study site by the Sponsor or Investigator may include but are not limited to:

- Failure of the Investigator to comply with the protocol, the requirements of the IRB/IEC or local health authorities, the Sponsor's procedures, or GCP guidelines.
- Inadequate recruitment of participants by the Investigator.
- Discontinuation of further study intervention development.

### 10.1.10 Publication Policy

- The results of this study may be published or presented at scientific meetings. If this is foreseen, the Investigator agrees to submit all manuscripts or abstracts to the Sponsor before submission. This allows the Sponsor to protect proprietary information and to provide comments.
- The Sponsor will comply with the requirements for publication of study results. In accordance with standard editorial and ethical practice, the Sponsor will generally support publication of multicenter studies only in their entirety and not as individual site data. In this case, a coordinating Investigator will be designated by mutual agreement.
- Authorship will be determined by mutual agreement and in line with International Committee of Medical Journal Editors authorship requirements.

## 10.2 APPENDIX 2: CLINICAL LABORATORY TESTS

The tests detailed in [Table 8](#) will be performed by the central laboratory.

- Protocol-specific requirements for inclusion or exclusion of participants are detailed in [Section 5](#) of the protocol.
- Additional tests may be performed at any time during the study as determined necessary by the Investigator or required by local regulations.

**Table 8 - Protocol-required laboratory assessments**

Laboratory assessments	Parameters			
Hematology	Platelet count	White blood cell (WBC) count with differential:		
	Red blood cell (RBC) count			
	Hemoglobin			
	Hematocrit			
		• Neutrophils		
		• Lymphocytes		
		• Monocytes		
		• Eosinophils		
		• Basophils		
Clinical chemistry a	Creatinine	Potassium	AST	Total bilirubin (if values above the normal range, differentiation in conjugated and non-conjugated bilirubin)
		Sodium	ALT	
	Albumin		Alkaline phosphatase	Estimated GFR (MDRD formula)
Efficacy laboratory	HbA1c	Glucose fasting		
Anti-insulin aspart	Anti-insulin aspart antibodies; if positive, titer, cross-reactivity to human insulin, and neutralizing capacity			

Laboratory assessments	Parameters
Other screening tests	

Follicle-stimulating hormone and estradiol (as needed in women of non-childbearing potential only)

Serum human chorionic gonadotropin (hCG) pregnancy test (as needed for women of childbearing potential) at Screening

Urine pregnancy testing will be performed subsequent to Screening. If the urine test is positive, serum <math>\beta</math>-hCG should be tested for confirmation of the pregnancyb

C-peptide

NOTES :

a Details of liver chemistry stopping criteria and required actions and follow-up assessments after liver stopping or monitoring event are given in [Section 10.5](#). All events of ALT >3 × upper limit of normal (ULN) and bilirubin >2 × ULN (>35% direct bilirubin) or ALT >3 × ULN and international normalized ratio (INR) >1.5, if INR measured which may indicate severe liver injury (possible Hy's Law) must be reported as an SAE

b Local urine testing will be standard for the protocol unless serum testing is required by local regulation or IRB/IEC.

ALT: alanine aminotransferase; AST: aspartate aminotransferase; GFR: glomerular filtration rate; HbA1c: glycated hemoglobin A1c; hCG: human chorionic gonadotropin; IEC: Independent Ethics Committee; INR: international normalized ratio; IRB: Institutional Review Board; MDRD: modification of diet in renal disease; ULN: upper limit of the normal; RBC: red blood cells; WBC: white blood cells.

Investigators must document their review of each laboratory safety report.

### 10.3 APPENDIX 3: ADVERSE EVENTS: DEFINITIONS AND PROCEDURES FOR RECORDING, EVALUATING, FOLLOW-UP, AND REPORTING

#### DEFINITION OF AE

##### AE definition

- An AE is any untoward medical occurrence in a patient or clinical study participant, temporally associated with the use of study intervention, whether or not considered related to the study intervention.
- NOTE: An AE can therefore be any unfavorable and unintended sign (including an abnormal laboratory finding), symptom, or disease (new or exacerbated) temporally associated with the use of study intervention.

##### Events meeting the AE definition

- Any abnormal laboratory test results (hematology, clinical chemistry, or urinalysis) or other safety assessments (eg, electrocardiogram [ECG], radiological scans, vital signs measurements), including those that worsen from baseline, considered clinically significant in the medical and scientific judgment of the Investigator (ie, not related to progression of underlying disease), ie:
  - Symptomatic, and/or
  - Requiring either corrective treatment or consultation, and/or
  - Leading to IMP/NIMP discontinuation or modification of dosing, and/or
  - Fulfilling a seriousness criterion, and/or
  - Defined as an AESI.

- Exacerbation of a chronic or intermittent pre-existing condition including either an increase in frequency and/or intensity of the condition.
- New conditions detected or diagnosed after study intervention administration even though it may have been present before the start of the study.
- Signs, symptoms, or the clinical sequelae of a suspected drug-drug interaction.
- Signs, symptoms, or the clinical sequelae of a suspected overdose of either study intervention or a concomitant medication.
- "Lack of efficacy" or "failure of expected pharmacological action" per se will not be reported as an AE or SAE. Such instances will be captured in the efficacy assessments. However, the signs, symptoms, and/or clinical sequelae resulting from lack of efficacy will be reported as AE or SAE if they fulfil the definition of an AE or SAE.
- The signs, symptoms, and/or clinical sequelae resulting from lack of efficacy will be reported as AE or SAE if they fulfil the definition of an AE or SAE. Also, "lack of efficacy" or "failure of expected pharmacological action" also constitutes an AE or SAE.

#### **Events NOT meeting the AE definition**

- Any clinically significant abnormal laboratory findings or other abnormal safety assessments which are associated with the underlying disease, unless judged by the Investigator to be more severe than expected for the participant's condition.
- The disease/disorder being studied or expected progression, signs, or symptoms of the disease/disorder being studied, unless more severe than expected for the participant's condition.
- Medical or surgical procedure (eg, endoscopy, appendectomy): the condition that leads to the procedure is the AE.
- Situations in which an untoward medical occurrence did not occur (social and/or convenience admission to a hospital).
- Anticipated day-to-day fluctuations of pre-existing disease(s) or condition(s) present or detected at the start of the study that do not worsen.

#### **DEFINITION OF SAE**

If an event is not an AE per definition above, then it cannot be an SAE even if serious conditions are met (eg, hospitalization for signs/symptoms of the disease under study, death due to progression of disease).

**A SAE is defined as any untoward medical occurrence that, at any dose:**

- a) Results in death.**
- b) Is life-threatening.**

The term "life-threatening" in the definition of "serious" refers to an event in which the participant was at risk of death at the time of the event. It does not refer to an event, which hypothetically might have caused death, if it were more severe.

**c) Requires inpatient hospitalization or prolongation of existing hospitalization.**

In general, hospitalization signifies that the participant has been detained (usually involving at least an overnight stay) at the hospital or emergency ward for observation and/or treatment that would not have been appropriate in the physician's office or outpatient setting. Complications that occur during hospitalization are AEs. If a complication prolongs hospitalization or fulfills any other serious criteria, the event is serious. When in doubt as to whether "hospitalization" occurred or was necessary, the AE should be considered serious.

Hospitalization for elective treatment of a pre-existing condition that did not worsen from baseline is not considered an AE.

**d) Results in persistent disability/incapacity.**

- The term disability means a substantial disruption of a person's ability to conduct normal life functions,
- This definition is not intended to include experiences of relatively minor medical significance such as uncomplicated headache, nausea, vomiting, diarrhea, influenza, and accidental trauma (eg, sprained ankle) which may interfere with or prevent everyday life functions but do not constitute a substantial disruption.

**e) Is a congenital anomaly/birth defect.**

**f) Other situations:**

- Medical or scientific judgment should be exercised in deciding whether SAE reporting is appropriate in other situations such as important medical events that may not be immediately life-threatening or result in death or hospitalization but may jeopardize the participant or may require medical or surgical intervention to prevent one of the other outcomes listed in the above definition. These events should usually be considered serious.

Examples of such events include:

- Invasive or malignant cancers, intensive treatment in an emergency room or at home for allergic bronchospasm, blood dyscrasias or convulsions that do not result in hospitalization, or development of drug dependency or drug abuse,
- Laboratory results that may indicate severe liver injury (possible Hy's Law, see [Table 8](#)).

## **RECORDING AND FOLLOW-UP OF AE AND/OR SAE**

### **AE and SAE recording**

- When an AE/SAE occurs, it is the responsibility of the Investigator to review all documentation (eg, hospital progress notes, laboratory reports, and diagnostics reports) related to the event.
- The Investigator will then record all relevant AE/SAE information in the eCRF.

- It is **not** acceptable for the Investigator to send photocopies of the participant's medical records to the Sponsor representative in lieu of completion of the AE/SAE eCRF page.
- There may be instances when copies of medical records for certain cases are requested by the Sponsor representative. In this case, all participant identifiers, with the exception of the participant number, will be redacted on the copies of the medical records before submission to the Sponsor representative.
- The Investigator will attempt to establish a diagnosis of the event based on signs, symptoms, and/or other clinical information. Whenever possible, the diagnosis (not the individual signs/symptoms) will be documented as the AE/SAE.

### Assessment of intensity

The Investigator will make an assessment of intensity for each AE and SAE reported during the study and assign it to 1 of the following categories:

- **Mild:** An event that is easily tolerated by the participant, causing minimal discomfort and not interfering with everyday activities.
- **Moderate:** An event that causes sufficient discomfort and interferes with normal everyday activities.
- **Severe:** An event that prevents normal everyday activities. An AE that is assessed as severe should not be confused with a SAE. Severe is a category utilized for rating the intensity of an event; and both AEs and SAEs can be assessed as severe.

An event is defined as "serious" when it meets at least 1 of the predefined outcomes as described in the definition of an SAE, NOT when it is rated as severe.

### Assessment of causality

- The Investigator is obligated to assess the relationship between study intervention and each occurrence of each AE/SAE.
- A "reasonable possibility" of a relationship conveys that there are facts, evidence, and/or arguments to suggest a causal relationship, rather than a relationship cannot be ruled out.
- The Investigator will use clinical judgment to determine the relationship.
- Alternative causes, such as underlying disease(s), concomitant therapy, and other risk factors, as well as the temporal relationship of the event to study intervention administration will be considered and investigated.
- The Investigator will also consult the Investigator's Brochure (IB) and/or Product Information, for marketed products, in his/her assessment.
- There may be situations in which an SAE has occurred and the Investigator has minimal information to include in the initial report to the Sponsor representative. However, **it is very important that the Investigator always makes an assessment of causality for every event before the initial transmission of the SAE data to the Sponsor representative.**

- The Investigator may change his/her opinion of causality in light of follow-up information and send a SAE follow-up report with the updated causality assessment.
- The causality assessment is one of the criteria used when determining regulatory reporting requirements.

### **Follow-up of AEs and SAEs**

- The Investigator is obligated to perform or arrange for the conduct of supplemental measurements and/or evaluations as medically indicated or as requested by the Sponsor representative to elucidate the nature and/or causality of the AE or SAE as fully as possible. This may include additional laboratory tests or investigations, histopathological examinations, or consultation with other health care professionals.
- If a participant dies during participation in the study or during a recognized follow-up period, the Investigator will make every effort to provide the Sponsor representative a copy of any post-mortem findings including histopathology.
- New or updated information will be recorded in the originally completed eCRF.
- The Investigator will submit any updated SAE data to the Sponsor within 24 hours of receipt of the information.

### **REPORTING OF SAEs**

#### **SAE reporting to the Sponsor representative via an electronic data collection tool**

- The primary mechanism for reporting an SAE to the Sponsor representative will be the electronic data collection tool.
- If the electronic system is unavailable for more than 24 hours, then the site will use the paper SAE data collection tool.
- The site will enter the SAE data into the electronic system as soon as it becomes available.
- After the study is completed at a given site, the electronic data collection tool will be taken off-line to prevent the entry of new data or changes to existing data.
- If a site receives a report of a new SAE from a study participant or receives updated data on a previously reported SAE after the electronic data collection tool has been taken off-line, then the site can report this information on a paper SAE form or to the Sponsor representative by telephone.

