Study intervention (IMP and NIMP administration)			←-----→						
Review of insulin dose		X	X	X	X	X	X		According to the Sponsor's instructions
Counting/collecting used and unused pens/Compliance check				X	X	X	X		
Diary data review and medical evaluation by Investigator		X	X	X	X	X	X		In addition to the scheduled visits, medical evaluation must also be performed in between visits, if data is available for review by the Investigator.
SMPG d	X	X	X	X	X	X	X		

	Screening		Open-label Treatment Period					Follow-up	Notes
Week	-2a	-1b	0 (D1)	4	8	12	16 EOTc	16 + 1 dayb	Visit Windows: Visit 1: 7 to 17 days before Visit 3; Visit 2: may be adjusted as appropriate to accommodate Visit 3 date; Visits 4 to 6: ±2 days; Visit 7: ±3 days; Visit 8: +2 days.
Day	-14a	-7	1	28	56	84	112	113	
Visit	1	2	3	4	5	6	7	8	
FPG			X		X	X	X		All fasting blood samples collections should take place prior to IMP administration.
Central laboratory									
PK sampling e							X		
HbA1c	X		X		X		X		
C-peptide (fasting)	X								
Anti-insulin aspart antibodies (AIA)			X		X	X	X		Antibody sampling at least 8 hours after the last SAR341402 or NovoLog dose, thus participants should come fasting, without injecting their meal-time insulin at all visits where AIAs are measured.
Anti-insulin aspart neutralizing antibodies			X		X	X	X		
Safety laboratory									
Hematology	X						X		See Appendix 2 ( Section 10.2 )
Clinical chemistry	X						X		See Appendix 2 ( Section 10.2 )
Pregnancy test (WOCBP only)	X		X		X		X		Serum pregnancy test for screening; urine pregnancy test for subsequent monitoring; additional testing per site's processes is permitted
Serum FSH and estradiol (Menopausal women only)	X								
AE/SAE/AESI reporting	Throughout the study								Report SAE and AESI to the Sponsor within 24 hours

	Screening		Open-label Treatment Period					Follow-up	Notes

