### 8.3.1 Time period and frequency for collecting AE and SAE information

All AEs and SAEs will be collected from the signing of the ICF until the follow-up visit.

All SAEs and AESI will be recorded and reported to the Sponsor or designee within 24 hours, as indicated in Appendix 3 ([Section 10.3](#)). The Investigator will submit any updated SAE data to the Sponsor within 24 hours of it being available.

Investigators are not obligated to actively seek AE or SAE after conclusion of the study participation. However, if the Investigator learns of any SAE, including a death, at any time after a participant has been discharged from the study, and he/she considers the event to be reasonably related to the study intervention or study participation, the Investigator must promptly notify the Sponsor.

The method of recording, evaluating, and assessing causality of AE and SAE and the procedures for completing and transmitting SAE reports are provided in Appendix 3 ([Section 10.3](#)).

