### **8.3.4 Regulatory reporting requirements for SAEs**

- Prompt (within 24 hour) notification by the Investigator to the Sponsor of an SAE is essential so that legal obligations and ethical responsibilities towards the safety of participants and the safety of a study intervention under clinical investigation are met.
- The Sponsor has a legal responsibility to notify both the local regulatory authority and other regulatory agencies about the safety of a study intervention under clinical investigation. The Sponsor will comply with country-specific regulatory requirements relating to safety reporting to the regulatory authority, Institutional Review Boards (IRB)/Independent Ethics Committees (IEC), and Investigators.
- Investigator safety reports must be prepared for suspected unexpected serious adverse reactions (SUSAR) according to local regulatory requirements and Sponsor policy and forwarded to Investigators as necessary.
- Adverse events that are considered expected will be specified in the reference safety information.
- An Investigator who receives an Investigator safety report describing a SAE or other specific safety information (eg, summary or listing of SAEs) from the Sponsor will review and then file it along with the Investigator's Brochure and will notify the IRB/IEC, if appropriate according to local requirements.

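### Appendix 3 names a paper back-up for SAE reporting only after an electronic outage of more than 24 hours, which is longer than the protocol's 24-hour reporting limit it has to serve

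*Protocol*

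**What the plan says.** **The deadline.** Protocol Section 8.3.1 states: "All SAEs and AESI will be recorded and reported to the Sponsor or designee within 24 hours, as indicated in Appendix 3". Section 8.3.4 repeats the limit for SAEs: "Prompt (within 24 hour) notification by the Investigator to the Sponsor of an SAE is essential". Both Schedules of Activities (1.3.1 without run-in, 1.3.2 with run-in) carry the same instruction in the AE/SAE/AESI row: "Report SAE and AESI to the Sponsor within 24 hours". Section 8.3 also defines an AESI as an event needing notification within 24 hours. Updated SAE data have the same limit in Appendix 3 itself: "The Investigator will submit any updated SAE data to the Sponsor within 24 hours of receipt of the information".

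**The route.** Appendix 3 (Section 10.3, Reporting of SAEs) says: "The primary mechanism for reporting an SAE to the Sponsor representative will be the electronic data collection tool". The next bullet gives the back-up: "If the electronic system is unavailable for more than 24 hours, then the site will use the paper SAE data collection tool". The site then enters the data electronically when the system is back.

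**The other paper or telephone route.** The last bullet covers SAE information received once the tool has been shut down because the study is complete at that site: "then the site can report this information on a paper SAE form or to the Sponsor representative by telephone". It does not cover an outage while the study is running.

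**The concern.** A back-up route exists so that a deadline can still be met when the main route fails. Here the back-up is stated to start only after a failure longer than the deadline. A site that turns to Appendix 3 during an outage, as Section 8.3.1 tells it to, finds an instruction that can take it past the limit set in Sections 1.3, 8.3.1 and 8.3.4.

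Two things are at stake. One is the timeliness of serious-event reports, which Section 8.3.4 ties to the sponsor's legal and ethical obligations. The other is that a site could be in deviation from one part of the protocol because it followed another part to the letter. AESIs are served less well still: they share the 24-hour limit, but the back-up sentence names only the SAE form.

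**Working it through.** The plan gives no figure to reproduce. The check compares its time rules.

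**Inputs from the protocol**
- Reporting limit: 24 h (Sections 1.3.1, 1.3.2, 8.3.1, 8.3.4).
- Primary route: the electronic tool (Appendix 3).
- Trigger for the paper form: an outage of more than 24 h (Appendix 3).
- Stated route during the first 24 h of an outage: none.

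**Assumptions**
- The clock starts when the site becomes aware of the event. Section 8.3.1 gives no start point for an initial report. Awareness fits the wording for updated data in Appendix 3, which counts from receipt of the information.
- The report has not been sent before the outage begins.
- The outage times below are illustrative; the documents give none.

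**Rule.** Set awareness at t = 0 and the deadline at t = 24 h. The outage starts at t = s and lasts D hours. The first route the text names opens at:
- s + D, if D ≤ 24 (the system returns and paper is never triggered);
- just after s + 24, if D > 24 (the paper form).

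The deadline is missed if that time is later than 24 h.

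| s (h) | D (h) | First stated route opens | Result |
|---|---|---|---|
| 0 | more than 24 | just after 0 + 24 = 24 h (paper) | missed, narrowly |
| 6 | 30 | just after 6 + 24 = 30 h (paper) | about 30 − 24 = 6 h late |
| 6 | 20 | 6 + 20 = 26 h (system back) | 26 − 24 = 2 h late, paper never triggered |
| 12 | 20 | 12 + 20 = 32 h (system back) | 32 − 24 = 8 h late, paper never triggered |
| −6 | 40 | just after −6 + 24 = 18 h (paper) | can be met, about 24 − 18 = 6 h left |
| 0 | 10 | 0 + 10 = 10 h (system back) | can be met, 24 − 10 = 14 h left |

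**General result**
- Outage starting at or after awareness (0 ≤ s < 24): the deadline is missed exactly when s + D > 24, that is, when the outage lasts past hour 24. As s runs from 0 to just under 24, the latest opening time, s + 24, runs from just after 24 h to just under 48 h.
- Outage starting before awareness (s < 0): the first stated route opens before hour 24, so the rule alone does not force a miss. If the outage started less than 24 h before awareness and lasts more than 24 h, the time left once paper opens is 24 − (s + 24) = −s hours, which is short when s is close to 0.

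**The case against.** The strongest reply is that the sentence in Appendix 3 says when the change to paper becomes mandatory and does not prohibit it sooner. The electronic tool is called the primary mechanism, not the sole one, and the 24-hour duty is nowhere suspended during an outage. A careful site reading the sections together would still notify in time. This stands as far as it goes: a reader might infer that paper is barred until 24 hours have passed, and the text does not say so. What remains is that no earlier route is named in the one place to which Section 8.3.1 refers the site.

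A second reply is that a miss needs an SAE, an outage beginning in the interval before the report is sent, and an outage running past the deadline. That is right. A reader might infer that the rule will produce late reports; the documents support only that it can.

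A third is that part of the lateness in the worst cases is the site's own. With s = 12 h the tool worked for 12 hours without a report being filed, and the figure near 48 h needs a site that waited almost the whole window. This also stands, although a site is within the limit for all of those hours.

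A fourth concerns consequences. There is no data monitoring committee (Section 9.5.1), and a reader might infer that these forms are the main real-time safety signal. The protocol does not say that. For possible Hy's Law cases there are other channels: chemistry is run centrally (Section 10.2), laboratory data are given as an example of electronic transfer to the sponsor (Section 10.1.7), and the site must tell the monitor about ALT increases (Section 10.5).

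Finally, separate site instructions may contain an earlier back-up. They are not among the documents and cannot be checked; if they do, the protocol text still needs to agree with them.

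**Conclusion.** The point holds as an internal inconsistency in safety reporting. The trigger for the stated back-up (more than 24 hours of outage) is longer than the limit it serves (24 hours), so this is wrong as written and not just missing detail. A site following Appendix 3 literally can report late when an outage begins at or after awareness, before the report is sent, and lasts past hour 24. The first stated route then opens somewhere between just after 24 h and just under 48 h after awareness.

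The conclusion about the trigger needs no assumption. The hour counts rest on awareness as the start of the clock and on illustrative outage times. No expected number of late reports can be given, because outage frequency and duration are not documented.

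The matter is operational. It has no bearing on the primary PK comparison, the analysis populations, the sample size or the error rates.

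**What to change.** In Appendix 3, Reporting of SAEs, delete the more-than-24-hours condition and reword the bullet along these lines: if the electronic system is unavailable, the site reports the SAE or AESI on the existing paper form or by telephone so that it reaches the sponsor within the 24-hour limit, and enters it electronically once the system is back. Naming AESIs and the telephone goes beyond the present sentence, but it brings the back-up into line with Sections 8.3 and 8.3.1. It would also help to state in Section 8.3.1 that the 24 hours run from the site's awareness of the event, if that is what is meant.

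The cost is a sentence or two in the protocol and a matching check of the site SAE instructions. The paper form already exists. The downside is occasional duplicate entry after short outages, which Appendix 3 already accepts by requiring later electronic entry.
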